	Screening ¹	Baseline Visit 1 ¹	Visit 2	Visit 3	Visit 4	Visit 5	Visit 6	Visit 7	ET Visit 8 ²	Safety Follow-up Visit 9
	Day -7 to -1	Week 1 Day 1	Week 1 Day 2	Week 4 ± 3 days	Week 8 ± 5 days	Week 12 ± 3 days	Week 16 ± 5 days	Week 20 ± 3 days	Week 24 ± 5 days	Week 28 ± 5 days
Evaluation	Site Visit	Site Visit	Site Visit	Telephone	Site Visit	Telephone	Site Visit	Telephone	Site Visit	Site Visit
Informed consent / assent	Х									
Eligibility review	Х	Х								
Demographics / medical history	Х									
Concomitant medications	Х	Х	Х	Х	Х	Х	Х	Х	Х	X
Adverse events	Х	Х	Х	Х	х	х	х	х	Х	x
Urinalysis / pregnancy test ³	Х	Х			Х		Х		Х	
12-Lead ECG (see Table 1-1)	Х	Х			Х				Х	
Holter Monitoring		Х			Х				Х	
Vital Signs (see Table 1-1)	х	Х	Х		Х		Х		х	
Physical exam ⁴	Х	Х	Х		Х		х		Х	
Dermatologic exam	х	Х	Х		Х		Х		х	Х
Digital photography⁵		Х			Х		х		Х	Х
VIIS (Investigator-assessed)		X ⁶	Х		х		х		Х	Х
Global impression of severity		Х			Х		х		Х	Х
Patient/Observer-reported scales ⁷		Х			Х		Х		х	х
PD sample collection ⁸		Х	Х		Х		Х		х	
Clinical laboratory testing ⁹	х	Х			Х		Х		х	
PK sample collection ¹⁰ (see Table 1-1)		Х	Х		Х		Х		Х	
Randomization		Х								
Administer study drug ¹¹		Х	Х	Х	Х	Х	Х	Х		
Dispense study drug & diary			Х		Х		Х			
Collect study drug & diary					Х		Х		Х	
Exit interview									X ¹²	

ECG = electrocardiogram; ET = early termination; PD = pharmacodynamic; PK = pharmacokinetic; VIIS = Visual Index for Ichthyosis Severity

1. Samples collected for urinalysis and clinical laboratory tests may be analyzed at a local lab.

- 2. Subjects who terminate early from the study will undergo, if possible, all of the assessments and procedures scheduled for Visit 8 (Week 24).
- 3. Urine pregnancy test for female subjects of child-bearing potential only. Tests can be analyzed at the study site.
- 4. Complete physical exam, including height and weight collection, performed at Screening Visit only; symptom directed physical exams at all other timepoints.
- 5. Subjects should refrain from bathing and applying study drug or as-needed topical symptom control therapy (emollients) to the treatment area within 12 hours of obtaining digital photographs.
- 6. VIIS must be independently assessed by two different Investigators at Baseline Visit 1 only.

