- 7. Patient-/caregiver-reported scales to be administered: EQ-5D-5L, global impression of severity, global impression of bother, global impression of treatment, itching, scratching, burden of bathing/showering, and Children's Dermatology Life Quality Index (CDLQI) / Dermatology Life Quality Index (DLQI).
- 8. PD assessments include skin cell samples and transepidermal water loss (TEWL) procedures.
- 9. Clinical laboratory includes hematology and chemistry. Refer to Sections 6.15.1.1 and 6.15.1.2 for more details.
- 10. PK sample collection (blood and urine) from approximately 16 subjects.
- 11. Study drug will be administered daily. At study visits when PK samples are collected, study drug may be administered at the study site after pre-dose PK samples have been obtained.
- 12. Exit interviews should be conducted within 30 days of Visit 8.

Visit			V	isit 1			Visit 2			Visit	s 4 and 8			Visit 6
Time (hours)	Pre- Dose	1	2	4	8	12	24	Pre- Dose	1	2	4	8	12	Pre- Dose
Window	-	± 15 min	± 60 min	-	± 15 min	± 15 min	± 15 min	± 15 min	± 15 min	-				
Adults (age ≥12 yea	ars old)													
12-Lead ECG	Х	Х	Х	Х	Х	Х		Х	Х	Х	Х	Х	Х	
Vital Signs	Х	Х	Х	Х	Х	Х	Х	Х	Х	Х	Х	Х	Х	Х
Blood PK Samples	Х	Х	Х	Х	Х	Х	Х	Х	Х	Х	Х	Х	Х	Х
Urine PK Samples	Х				Х			Х				Х		
Children (age < 12	years old	d)												
12-Lead ECG	Х	Х		Х				Х	Х		Х			
Vital Signs	Х	Х		Х			Х	Х	Х		Х			Х
Blood PK Samples	Х	Х		Х			Х	Х	Х		Х			Х
Urine PK Samples	Х			Х				Х			Х			

Table 2-1. Part 2 Pharmacokinetic and Cardiac Monitoring

TABLE OF CONTENTS

IN	VESTIC	SATC	R STATEMENT	2
SY	'NOPSI	S		3
ΤA	BLE OI	F CO	NTENTS	11
LIS	ST OF 1	ΓABL	ES	15
LIS	ST OF A	\BBF	REVIATIONS AND DEFINITION OF TERMS	16
1		IN	IRODUCTION	18
	1.1	Sjö	gren-Larsson Syndrome	18
	1.2	Th	erapeutic Rationale for ADX-102 in Sjögren-Larsson Syndrome	18
	1.3	Cli	nical Trials of ADX-102	19
	1.3	3.1	Sjögren-Larsson Syndrome	19
	1.3	3.2	Ocular Indications	20
	1.4	Mir	nimization of Risk	20
	1.5	Po	tential Benefit	20
	1.6	Ra	tionale for Dose Selection	21
2		ST	UDY OBJECTIVES AND ENDPOINTS	21
	2.1	Stu	udy Objectives	21
	2.1	1.1	Primary Objective	21
	2.1	1.2	Secondary Objective	21
	2.2	Stu	udy Endpoints	21
	2.2	2.1	Primary Endpoint	21
	2.2	2.2	Secondary Endpoints	21
3		IN	/ESTIGATIONAL PLAN	22
	3.1	Ov	erall Study Design and Plan	22
	3.2	As	signing Subjects to Treatment Groups	23
	3.2	2.1	Subject Numbering	23
	3.2	2.2	Randomization	23
	3.3	Bli	nding and Unblinding	23
	3.3	3.1	Blinding	23
	3.3	3.2	Emergency Unblinding	23
	3.4	Sa	fety Oversight	24

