6.15.1 Laboratory Parameters

Samples of blood and urine will be collected for clinical laboratory tests which includes general safety parameters (hematology, serum chemistry, and urinalysis) and pregnancy tests.

Blood samples for laboratory assessments will be collected at the site by the Investigator, or qualified study personnel.

Samples collected at the Screening Visit may be analyzed at a local lab. All other samples will be shipped to a central laboratory. Full details of equipment and procedures for laboratory testing will be listed in the Laboratory Manual.

The Investigator must categorize all abnormal urine, hematology and chemistry laboratory values as either clinically significant (CS) or not clinically significant (NCS). Clinical significance is defined as any variation in laboratory parameters, which has medical consequences that result in an alteration in the subject's medical care. In case of CS laboratory results, the Investigator will continue to monitor the subject with additional laboratory assessments until values have reached normal range and/or baseline levels. CS laboratory results should be reported as an adverse event in accordance with Section 9.

Biological material will be stored and secured in a manner that ensures that unauthorized access is prohibited and the samples are not lost, allowed to deteriorate, or accidentally or illegally destroyed.

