8.1 Screening Visit (Day -7 to -1) – Site Visit

- Obtain written informed consent/assent (Section 6.1)
- Review eligibility criteria (Section 6.2)
- Collect demographic information and document medical history (Sections 6.3)
- Record concomitant medications and adverse events (Sections 6.4 and 6.5)
- Collect urine sample for urinalysis¹ and pregnancy test, if applicable (Sections 6.15.1.3 and 6.15.1.4)
- 12-lead ECG (Section 6.6)
- Collect vital signs (Section 6.7)
- Complete physical examination, including height and weight collection (Section 6.8)
- Complete dermatologic examination (Section 6.12)
- Collect blood samples for hematology and chemistry⁹ (Sections 6.15.1.1 and 6.15.1.2)

¹ Samples collected for urinalysis and clinical laboratory tests at the Screening Visit may be analyzed at a local lab.

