8.2 Baseline Visit 1 (Week 1/Day 1) – Site Visit

- Collect Patient/Observer-reported scales (Section 6.11)
- Review eligibility criteria (Section 6.2)
- Record concomitant medications and adverse events (Sections 6.4 and 6.5)
- Collect urine sample for urinalysis and pregnancy test, if applicable (Sections 6.15.1.3 and 6.15.1.4)
- 12-lead ECG and Holter monitoring (Section 6.6)
- Collect vital signs (Section 6.7)
- Symptom-directed physical exam (Section 6.8)
- Complete dermatologic examination (Section 6.12)
- Take digital photography (Section 6.13)
- Complete VIIS (Section 6.9)
- Complete clinician-reported global impression of severity scale (Section 6.10)
- PD sample collection (Section 6.14)
- Collect blood samples for hematology and chemistry (Sections 6.15.1.1 and 6.15.1.2)
- PK sample collection (blood and urine) (Section 6.16)
- Randomize subject (Section 6.18)
- Apply study drug to all areas of ichthyosis (Section 5.6)

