11.3. CLINICAL LABORATORY EVALUATIONS

Laboratory tests will be performed at Screening and periodically throughout the clinical trial as described in the schedule of events, Section 4. Only data collected by the central laboratory will be included in the analyses with the exception of the screening safety data. Standard international units will be used for all summaries. Laboratory tests within each category and scheduled visit are given in Table 9.4.1. Data for all visits, scheduled or unscheduled, will be listed.

At least one laboratory measurement obtained subsequent to at least one dose of Study Treatment is required for inclusion in the analysis of each specific parameter. To assess change from baseline, a baseline or screening measurement is also required.

Table 11.3.2: Laboratory Tests and Scheduled Study Visits

Laboratory Category	Laboratory Tests Included	
Hematology	hemoglobin, hematocrit, red blood cell (RBC) count, RBC morphology, white blood cell (WBC) count with differential, mean corpuscular volume (MCV), mean corpuscular hemoglobin (MCH), mean corpuscular hemoglobin concentration (MCHC), and absolute platelet count.	
Chemistry	albumin, alkaline phosphatase (ALP), alanine aminotransferase (ALT; SGPT), aspartate aminotransferase (AST; SGOT), bilirubin (total and direct), blood urea nitrogen (BUN), calcium, carbon dioxide (CO2), chloride, creatinine, creatinine phosphokinase (CPK), glucose, phosphate, potassium, sodium, total protein, and uric acid.	
Urinalysis	bilirubin, glucose, ketones, blood, nitrite, pH, protein, specific gravity, and microscopy (if indicated by macroscopic findings).	
Other	Urine Pregnancy Test for Female Subjects	
Estimated Glomerular Filtration Rate (eGFR)	Adult population (≥ 18 years of age): eGFR will be calculated by the MDRD equation at baseline:	

Syneos Health #1009367

eGFR (mL/min/1.73 m2) = $175 \times (Scr)-1.154 \times (Age)-0.203 \times (0.742 \text{ if female}) \times (1.212 \text{ if African American}) \text{ (Levey 2009)}$	
Pediatric population (3 - < 18 years of age): eGFR will be calculated by the Schwartz equation at baseline:	
eGFR (mL/min/1.73 m ²) = $(0.41 \times \text{Height in cm})$ / Creatinine in mg/dL (Schwartz 2009)	

- Actual (observed) values and changes from baseline in hematology and clinical chemistry laboratory parameters will be summarized by treatment group at each scheduled visit

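### Table 2 allows local-laboratory analysis of Part 2 baseline safety samples, contradicting Section 6.15.1, so laboratory change from baseline can include a between-laboratory difference

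*Protocol*

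**What the plan says.** Protocol Table 2 heads its second visit column "Baseline Visit 1 ¹", and the Screening column carries the same mark. Footnote 1 to that table states: "Samples collected for urinalysis and clinical laboratory tests may be analyzed at a local lab". Footnote 9 defines the blood tests concerned: "Clinical laboratory includes hematology and chemistry". These tests and urinalysis are scheduled at Screening, Baseline, Visit 4 (Week 8), Visit 6 (Week 16) and Visit 8 (Week 24).

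Protocol Section 6.15.1 gives a different rule: "Samples collected at the Screening Visit may be analyzed at a local lab. All other samples will be shipped to a central laboratory". The opening of Section 6 applies its procedures to both Parts unless stated otherwise.

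For Part 2, the footnote to Section 8.1 reads "Samples collected for urinalysis and clinical laboratory tests at the Screening Visit may be analyzed at a local lab". Section 8.2, which covers Baseline Visit 1, lists the same blood and urine samples with no local option. In Part 1, Table 1 attaches the equivalent footnote to Screening only.

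On analysis, protocol Section 10.5.1 plans descriptive laboratory summaries by arm and time, or change tables for categorized variables such as normal versus abnormal. The SAP covers Part 1 only (SAP Section 2). For Part 1, SAP Section 11.3 says "Only data collected by the central laboratory will be included in the analyses with the exception of the screening safety data" and "To assess change from baseline, a baseline or screening measurement is also required".

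**The concern.** Change from baseline in a laboratory value describes what happened on treatment only if both measurements come from comparable methods. If the pre-dose sample is read locally and every on-treatment sample centrally, a difference in assay or reference range enters at the first on-treatment visit and stays. Within an arm, that pattern looks the same as a sustained drug effect. A normal-versus-abnormal change table is open to the same problem, because the category depends on a reference range.

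The baseline is used in other places too. Section 6.15.1 names baseline levels as one of the end points for following up a clinically significant result. Section 10 presents safety data from the two Parts by stratum and overall, so the overall tables could combine subjects with central baselines and subjects with local ones.

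What is at stake is how clearly the descriptive safety laboratory data of Part 2 can be read, in a Part that applies the cream to about 80-90% of body surface for 24 weeks.

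**Working it through.** No arithmetic applies to the contradiction. The check is to set the provisions side by side and follow each reading through to the analysis.

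**Where may a Part 2 Day 1 safety sample be analyzed?**

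| Source | Local analysis on Day 1? |
|---|---|
| Table 2, footnote 1 on the Baseline Visit 1 column | Allowed |
| Section 6.15.1 (both Parts) | No; central |
| Section 8.1 footnote | Local option limited to Screening |
| Section 8.2 | No local option given |
| Table 1 (Part 1, for comparison) | Footnote on Screening only |

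One provision allows it. Section 6.15.1 forbids it, and the other three fit with 6.15.1.

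**What follows for laboratory change in Part 2?**

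1. *Section 6.15.1 is followed.* Day 1 and Weeks 8, 16 and 24 are all central. Two laboratories are compared only if the Day 1 value is missing and a local Screening value takes its place.
2. *Table 2 is followed.* Screening and Day 1 may both be local, and Weeks 8, 16 and 24 are central under 6.15.1. For such a subject, every change from baseline compares two laboratories.
3. *Table 2 is followed and the Part 1 SAP rules are carried over.* SAP Section 8.4 takes the latest available pre-dose value as baseline, with no condition on the laboratory. SAP Section 11.3 admits non-central data only from Screening. A local Day 1 value would be dropped, and a Screening value that may also be local would replace it. The two-laboratory comparison remains.

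The existing SAP rules therefore do not remove the problem created by reading 2.

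**How large is it?** Local analysis is optional, so the share of Part 2 subjects affected could lie anywhere from 0% to 100%. The documents give no between-laboratory difference for any analyte, so no size in laboratory units can be computed. Protocol Section 10.1 expects 20 active and 10 vehicle subjects, and the synopsis expects about 8 centers, which averages 10 / 8 = 1.25 vehicle subjects per center. Section 3.2.2 mentions no stratification by site. Chance imbalance between arms in which local laboratories were used is therefore possible, but its direction and size are unknown.

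**The case against.** The strongest reply is that this is one stray superscript. Section 6.15.1 is the governing procedure and is explicit, the visit-by-visit text agrees with it, and other footnote marks in Sections 7.1, 8.1 and 8.7 match no note in their own section. The mark may simply be an editing slip. That is plausible, but a site may well work from the schedule table, and there the mark gives a clear permission. If a site acts on it, the central pre-dose value never exists.

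A second reply is that local analysis on Day 1 may be deliberate. Eligibility is reviewed again at Baseline, and exclusion 9 concerns clinically significant laboratory abnormalities. This stands as a possibility. It would justify a local result in addition to a central one, but not in place of it.

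A third reply is that the stakes are modest. No inferential safety testing is planned, and the primary endpoint, sample size and efficacy claim rule are unaffected. All of that stands.

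Four stronger inferences are tempting and should not be drawn:

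- **That the SAP's shift tables and its baseline-or-screening rule are settled Part 2 methods.** The SAP is limited to Part 1. Protocol Section 10 anticipates largely common analyses for the two Parts, which makes a carry-over likely, but no Part 2 plan is among the documents.
- **That the comparison between arms is biased.** A local-to-central step would arise in both randomized arms, and the vehicle column would show it too. Chance imbalance is possible; systematic bias is not shown.
- **That the Part 1 treatment interruptions for laboratory findings (SAP Section 8.6) are connected with this.** They show that laboratory data matter for this product. Table 1 does not have the conflict.
- **That the Part 1 fallback to Screening is itself a defect.** It applies only when Day 1 is missing and is consistent with the SAP's baseline definition. With about 9 subjects, dropping such cases from the change tables is a debatable trade.

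**Conclusion.** The contradiction is real and the point holds within limits. Table 2 allows what Section 6.15.1 excludes, and every other relevant provision fits with 6.15.1. If Table 2 is followed, a Part 2 subject may have no central safety laboratory value before dosing, and that subject's descriptive changes at Weeks 8, 16 and 24 can include a between-laboratory difference of unknown size.

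This rests on three assumptions: that some sites use the Table 2 permission, that the Laboratory Manual (not among the documents) does not override it, and that the Part 2 report presents laboratory change from a pre-dose value, as Section 10.5.1 suggests. Whether normal-versus-abnormal tables are distorted also depends on whether each value is classified against its own laboratory's range, which the documents do not say.

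The effect is confined to descriptive safety data and does not bear on efficacy. It merits correction because the loss would be permanent and prevention is cheap.

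**What to change.** - **Protocol Table 2:** remove footnote 1 from the Baseline Visit 1 column, so that Day 1 hematology, chemistry and urinalysis samples go to the central laboratory as Section 6.15.1 requires. Pregnancy tests are separate; Table 2 footnote 3 already allows them at the site.
- **If a local Day 1 result is wanted for eligibility:** say so, and send a Day 1 sample to the central laboratory as well.
- **Part 2 analysis plan:** use the central Day 1 value as the laboratory baseline, and flag any change or shift that rests on a local pre-dose value.
- **Part 1:** the Screening fallback for a missing baseline need not change.

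The cost is one superscript in the protocol and about a sentence in the Part 2 plan. The duplicate-sample option adds a shipment and some blood, which counts toward the volume limits in Section 6.15. Because affected subjects are flagged and not excluded, none is lost from the tables.

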CDLQI	Children's Dermatology Life Quality Index
CI	Confidence interval
CNS	Central nervous system
CO ₂	Carbon dioxide
CFR	Code of Federal Regulations
COA	Clinical outcomes assessments
CPK	Creatinine phosphokinase
CR	Central Reader
CRF	Case report form
CRO	Contract Research Organization
CS	Clinically significant
DLQI	Dermatology Life Quality Index
DNA	Deoxyribonucleic acid
DSMB	Data Safety Monitoring Board
ECG	Electrocardiogram
EDC	Electronic data capture
ET	Early termination
FALDH	Fatty aldehyde dehydrogenase
FDA	Food and Drug Administration
GCP	Good Clinical Practice
GEE	Generalized Estimated Equation
GLP	Good Laboratory Practice
HEENT	Head, eyes, ears, nose, and throat
HR	Heart rate
ICH	International Council on Harmonisation
IEC	Independent Ethics Committee
IP	Intraperitoneal

LIST OF ABBREVIATIONS AND DEFINITION OF TERMS

IRB	Institutional Review Board
IRT	Interactive Response Technology
ISS	Ichthyosis Severity Score
IV	Intravenous
MCH	Mean corpuscular hemoglobin
MCHC	Mean corpuscular hemoglobin concentration
MCV	Mean corpuscular volume
MedDRA	Medical Dictionary for Regulatory Activities
MMRM	Mixed model repeated measures
NCS	Not clinically significant
PI	Principal Investigator
PD	Pharmacodynamic
PK	Pharmacokinetic
PH	Proportional hazards
PO	Oral
RBC	Red blood cell
REB	Research Ethics Board
RR	Respiratory rate
SAE	Serious adverse event
SAP	Statistical analysis plan
SC	Subcutaneous
SD	Standard deviation
SLS	Sjögren-Larsson Syndrome
SOP	Standard Operating Procedure
SUSAR	Suspected unexpected serious adverse reaction
TD	Topical dermal
TEAE	Treatment-emergent adverse event
TEWL	Transepidermal Water Loss
ТО	Topical ocular
VIIS	Visual Index for Ichthyosis Score
WBC	White blood cell

1 INTRODUCTION

1.1 Sjögren-Larsson Syndrome

ADX-102 1% is being developed for the treatment of ichthyosis associated with Sjögren-Larsson Syndrome (SLS). SLS (ICD Q87.1) is a rare, chronically-debilitating, autosomal-recessive disorder characterized by generalized ichthyosis, cognitive deficit in a majority of patients, and spastic diplegia or tetraplegia. SLS is caused by mutations in the *ALDH3A2* gene that encodes fatty aldehyde dehydrogenase (FALDH), an enzyme that catalyzes the oxidation of aliphatic aldehydes to fatty acids (3).

In most patients, ichthyosis (dry, thickened, scaly, erythematous skin that is pruritic and, due to frequent excoriation, friable) is moderate or severe, particularly prominent in flexure areas, and involves much of the body surface except the face and glabrous skin (3). The dermal symptoms are generally recalcitrant to therapy, and are associated with significant daily physical and emotional burden and social stigma for patients and caregivers. The cutaneous symptoms are apparent at birth in almost all patients; they become more established by several months of age and remain throughout life (2). Developmental delay, spasticity, and other neurological symptoms become apparent over the first 2 years of life. The onset of neurologic symptoms usually prompts recognition of a diagnosis of SLS rather than another type of ichthyotic disorder (2).

SLS ichthyosis pathophysiology is well understood; fatty aldehydes disrupt dermal function, particularly the epidermal fatty moisture barrier, resulting in pathologic water loss, cutaneous desiccation, and compensatory keratinocytic hypertrophy (1). In epidermal cells, FALDH deficiency results in impaired oxidation of long-chain fatty aldehydes to fatty acids. The consequent accumulation of aldehydes disrupts the normal function and secretion of lamellar bodies and leads to intercellular lipid deposits in the stratum corneum and a defective water barrier in the skin layer, resulting in the cutaneous symptoms of SLS (2).

Ichthyosis related to SLS is a serious disease and there is no currently approved treatment that targets the underlying disease. Bathing several hours per day and over-the-counter moisturizing creams are the main interventions used to attempt to treat the symptoms, but have only limited and variable results, lasting for no more than a few hours. Keratolytic agents, salicylic acid, and urea are also considered for treatment. Patients with severe ichthyosis who are unresponsive to topical agents typically receive treatment with systemic retinoids, which are associated with a variety of toxicities. Patients are not usually maintained on retinoids due to concerns about toxicity, particularly in pediatric patients. No clinical intervention has been well studied in SLS patients, and therapeutic efficacy is generally variable. There is considerable social stigma in SLS since the skin appearance resembles disseminated cutaneous infectious disease and scales often emit a foul odor due to bacterial overgrowth and putrefaction.

